## 1. Study Summary

Study Title	Randomized Controlled Trial To assess the Benefits of Dexcom Continuous Glucose Monitoring with Glucose telemetry System for the Management of Diabetes in Long-term Care Setting: The CGM-GTS in Long-term care
Study Design	Randomized Controlled Trial
Primary Objective	To compare differences in frequency of hypoglycemia (<70 mg/dl) and glycemic control (time in range [TIR] 80-180 mg/dl) between the Dexcom CGM with Glucose Telemetry System (CGM-GTS) compared to a standard of care protocol, in residents with T2D treated with insulin and/or insulin-secretagogues, in subacute and long-term skilled nursing care facilities.
Secondary Objective(s)	Determine differences in clinical outcomes (number of complications, ER visits and need for hospital re-admissions), and health care utilization between the use of real-time Dexcom CGM Glucose Telemetry System (CGM-GTS) compared to a standard of care in patients with T2D in subacute and long-term skilled nursing care facilities.
Research Intervention(s)/Interactions	POC testing or to real time Dexcom CGM with GTS for up to 60 days of admission.
Study Population	Adult residents with T2D in subacute and long-term skilled nursing care facilities treated residents with T2D treated with insulin and/or insulin-secretagogues.
Sample Size	100
Study Duration for individual participants	Length of admission to subacute and long-term skilled nursing care facilities or up to 60 days (whichever comes sooner)
Study Specific Abbreviations/ Definitions	T2DM: Type 2 Diabetes Mellitus OADs: oral antidiabetic medications CGM: continuous glucose monitor GTS: glucose telemetry system LTC: Long Term Care SSI: Sliding Scale Insulin
Funding Source (if any)	Dexcom, Inc.

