## 6. Procedures Involved

Residents with T2D in subacute and long-term skilled nursing care facilities treated with insulin and/or insulin-secretagogues will be randomized to a standard of care group with POC testing or to real time Dexcom CGM with GTS for up to 60 days of admission.

Patients in the standard of care group will wear a blinded CGM and receive POC testing before meals and bedtime, with providers adjusting oral agents or insulin dose based on POC results. Patients in the intervention CGM group will have a single daily fasting POC testing and will wear a real-time Dexcom G6 with GTS, and providers will adjust oral or insulin therapy based on CGM-GTS profile information.

Nursing staff and primary care will receive education on the CGM technology by our research team.

Education efforts will include general information on the technology, how and when to remove or replace CGM sensors and transmitters, and the hypoglycemia prevention protocol. Treatment of hypoglycemia (POC <70 mg/dl) will be similar in both groups following a standard hospital protocol.

[figure not shown]
CGM alarm settings, and prevention of hypoglycemia protocol. Hypoglycemia alarm will be set to < 85 mg/dl (for prevention for low blood glucose levels). Nursing staff will be instructed to provide 15 grams of carbohydrates in response to a hypoglycemia alarm. For control group (blinded CGM) CGM alarms are turned off, however if the POC is found to be between <80 mg/dl by POC, 15 grams of carbohydrates will be given as a preventive measurement for hypoglycemia (standard of care).

The hyperglycemia alarm will be set at 300 mg/dl. If this occurs, the nursing staff will assess clinical status and perform a POC glucose testing to confirm glucose values. If BG > 300 mg/dl, nursing staff will communicate the high glucose value to the primary care team.

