## 9. Study Timelines

The duration of an individual participant's participation in the study will be equal the length of admission to subacute and long-term skilled nursing care facilities (LTC) or up to sixty (60) days, whichever comes sooner.

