### Inclusion Criteria:

1. Males and females admitted to subacute and long-term skilled nursing care facilities
2. Known history of T2D treated with insulin (glargine, detemir, degludec, NPH, premixed insulin) or sliding scale regular insulin) or insulin secretagogues (sulfonylureas, repaglinide, nateglinide) with or without additional oral antidiabetic agents (alpha-glucosidase inhibitors, thiazolidinedione, SGLT2- inhibitors, DPP4-inhibitors), short- and long-acting GLP1-RA (exenatide, liraglutide, dulaglutide, semaglutide)
3. Patients with an expected LTC length-of-stay > 1 week

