### **24. Resources Available**

Potential subjects will be identified by their treating physicians and referred to the researchers. Residents' private and identifiable information will not be shared prior to receiving permission from the resident to do so. All residents with history of diabetes will be considered for participation. The research team and/or the research coordinators will also review resident's medical records and laboratory tests to identify potential candidates. Once identified, the investigators and/or research coordinators will discuss the protocol with the attending physician taking care of the resident and request permission to include him/her in the trial. If the primary physician agrees to include the resident in the trial, then the resident will be invited to participate in the study. Potential candidates will be informed that there are other forms for glucose monitoring available to manage their diabetes. Long-term care residents will be instructed both verbally and in the written informed consent form that their participation in the study is entirely voluntary and that they can withdraw at any time, which will in no way compromise or alter the usual care that they would otherwise receive. They will also be given the phone numbers of the PI, IRB chair and Grady official to whom they can address any questions or concerns.

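### Neither the one-week stay criterion nor the 60-day limit is anchored to randomization, so residents close to discharge can qualify with only a few days of CGM

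*Combined protocol and SAP*

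**What the plan says.** Section 10, inclusion criterion 3, reads "Patients with an expected LTC length-of-stay > 1 week". It names no starting point for the stay.

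The 60-day limit appears in three places. Section 1 gives the intervention as "POC testing or to real time Dexcom CGM with GTS for up to 60 days of admission". Section 6 describes the randomized monitoring in nearly the same terms: "real time Dexcom CGM with GTS for up to 60 days of admission". Section 9 equates the time in the study with the stay, in that "participation in the study will be equal the length of admission", and then caps it with the words "or up to sixty (60) days, whichever comes sooner". None of them says on which day the count begins.

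Section 4 assesses both primary outcomes over the admission, without a window dated from randomization. Section 24 adds "All residents with history of diabetes will be considered for participation", and no section limits how long after admission a resident may be enrolled. In Section 18 the first safety analysis compares the proportions with at least one episode. The Poisson or negative binomial models that follow have no stated offset for time observed.

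**The concern.** Length of stay ordinarily means the whole stay. On that reading, a subacute resident screened on day 7 of an expected 9-day stay satisfies criterion 3 and yields 9 - 7 = 2 days of CGM. The chance of at least one episode depends directly on how long a resident is observed. Someone watched for two or three days contributes few events in either arm, yet takes a full place in a total of 100 (Section 12) and pulls the two proportions together. The same resident supplies a noisy time-in-range value that counts as much as one based on 60 days.

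The undefined start of the 60 days adds a second source of uneven follow-up. Section 23 names three facilities, and nothing in the text stops them from counting differently.

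**Working it through.** **The plan's own figure.** Section 18 gives 70 per group for 60% versus 35% at 80% power. With mean proportion 0.475 and two-sided alpha 0.05 (alpha is not stated in the plan):

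n = [1.960 × √(2 × 0.475 × 0.525) + 0.842 × √(0.60 × 0.40 + 0.35 × 0.65)]² / 0.25² = 61.4, so 62.

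With the continuity correction: (61.4/4) × [1 + √(1 + 4/(61.4 × 0.25))]² = 69.2, so 70. The same formula gives 49, 70, 107, 186 and 408 across the table, against the stated 49, 70, 107, 186 and 407. The figure is reproduced, although the text calls the method a one-sided t-test. Follow-up time does not enter the calculation, so the plan's number takes no account of short stays.

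**Inputs for the illustration**
- Event rates of 60% and 35%, from Section 18. The text there attaches 35% to standard of care, while the table heading attaches it to CGM. The table is followed here. With equal arms and a two-sided test, swapping the labels leaves power unchanged.
- 50 per arm: the total of 100, assuming 1:1 allocation (the ratio is not stated).
- Assumed: constant daily hazard, and 60%/35% reached after R days.
- Assumed: a share f of residents has only T = 2 or 3 days, and the rest have R days.
- Test: uncorrected two-sided chi-square at 0.05, with exact binomial power.

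**Formulas**
- Risk at T days: control 1 - 0.40^(T/R), CGM 1 - 0.65^(T/R).
- Mixed rate: (1 - f) × full rate + f × short-stay rate.

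**One case in full, R = 30 and T = 3**
- Hazards: -ln(0.40)/30 = 0.0305 and -ln(0.65)/30 = 0.0144 per day.
- Three-day risks: 8.8% and 4.2%.
- f = 0: 60% vs 35%, power 73.4%.
- f = 0.10: 0.9 × 60 + 0.1 × 8.8 = 54.9% vs 0.9 × 35 + 0.1 × 4.2 = 31.9%, power 66.2%.
- f = 0.20: 49.8% vs 28.8%, power 58.4%.

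**Range over R and T**

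| R (days) | T (days) | Short-stay risk, control / CGM | Power, f = 10% | Power, f = 20% |
|---|---|---|---|---|
| 5 | 2 | 31% / 16% | 70% | 66% |
| 5 | 3 | 42% / 23% | 72% | 70% |
| 10 | 2 | 17% / 8% | 68% | 61% |
| 10 | 3 | 24% / 12% | 69% | 64% |
| 20 | 2 | 9% / 4% | 66% | 58% |
| 20 | 3 | 13% / 6% | 67% | 60% |
| 30 | 2 | 6% / 3% | 66% | 57% |
| 30 | 3 | 9% / 4% | 66% | 58% |
| 60 | 2 | 3% / 1% | 65% | 56% |
| 60 | 3 | 4% / 2% | 65% | 57% |

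R is spread widely because the plan's rates have no common time base. The 60% is argued from a hospital CGM trial whose duration is not given. The only hospital CGM stay reported in Section 3 is a median of 5 days, in a different series. The 35% is attributed to a long-term care trial that Section 3 describes as lasting 6 months. The protocol's own cap is 60 days.

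**The case against.** The criterion speaks of expected stay, which is judged at screening, and a coordinator could fairly take it to mean a week still ahead. The Section 24 sentence concerns recruitment and is subject to the Section 10 criteria. It is not a rule on timing. Both points are fair. They show that the wording is ambiguous, but they supply no minimum follow-up.

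A reader might infer from "real time Dexcom CGM with GTS for up to 60 days of admission" that the 60 days run from facility admission, so that a long-stay resident's period could be over before enrolment. The documents do not support this. Section 9 describes the duration of participation, which cannot begin before enrolment, and Section 6 attaches the 60 days to the monitoring to which residents are randomized. The inferred reading would also leave many residents with no study period in a trial that recruits from long-term care. What stands is only that day 0 is unstated.

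A reader might also infer bias. Randomization balances short stays between arms on average, so eligibility wording alone does not create it. Bias would need discharge or transfer to depend on arm, and the documents give no evidence of that.

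Finally, the short-stay share, the 2-3 days and the reference time are all assumed. If the plan's rates are reached within 5 to 10 days, short-stay residents still have a material chance of an event, and the loss is smaller: power of 68-72% at a 10% share and 61-70% at 20%. That objection stands, and the range quoted here includes those cases.

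**Conclusion.** The point holds as a gap in definition. Criterion 3 does not secure any follow-up after randomization, and the 60-day limit has no stated start. The consequence is dilution of the at-least-one-episode comparison and uneven precision in time in range. Under the stated assumptions, power at 50 per arm falls from 73% to about 65-72% with a 10% short-stay share and to 56-70% with 20%. These figures show the sensitivity of the design and do not forecast the loss in this trial, since the share of residents near discharge cannot be obtained from the documents. The change is worth making because it costs little, and because the planned total of 100 is already below the 70 per group that Section 18 calculates.

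**What to change.** 1. In Section 10, reword criterion 3 as *expected remaining stay of more than one week after randomization*.
2. Define day 0 as randomization. Make Sections 1, 4, 6 and 9 all count from randomization until facility discharge or day 60, whichever is sooner.
3. Count primary outcomes from randomization. Starting at sensor insertion would drop POC-detected episodes before insertion, although Section 18 analyses hypoglycemia by both POC and CGM. It would also leave any resident never fitted with a sensor without an outcome.
4. In Section 18, add the log of follow-up time, or of CGM-wear time for CGM-detected events, as an offset in the planned Poisson or negative binomial models. Follow-up will still vary between residents after the rewording. The offset does not help the comparison of proportions, so the eligibility change is needed as well.

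The cost is a few wording changes and a record of observed time per resident. A few residents near discharge become ineligible, so screening takes slightly longer.

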### Exclusion Criteria:

1. Patients expected to require MRI procedures during admission.
2. Patients with clinically relevant hepatic disease (diagnosed liver cirrhosis and portal hypertension), corticosteroid therapy, end-stage renal disease (dialysis), or anasarca (massive peripheral edema).

3. Female subjects who are pregnant or breast-feeding at time of enrollment into the study.

**Inclusion of children:** No patients under the age of 18 will be recruited in this study.

### **11. Vulnerable Populations:**

Prisoners, pregnant women, neonates will not be included in the study. Nursing home residents with diabetes have higher rates of serious comorbidities and have greater activity of daily living dependencies than other residents without diabetes. The present study aims to determine if CGM -GTS will benefit the management and reduce the risk of hypoglycemia of LTC patients with T2DM. Research staff will ask the primary care team about the resident's cognitive status and ask if they are able to consent. If the primary team deems the patient is not able to give informed consent then we will approach the legal representative (durable power of attorney for health care, court appointed guardian for health care decisions, spouse, or adult child).

### **12. Local Number of Participants**

*The total number of participants to be accrued locally is 100.*

### **13. Recruitment Methods**

Coordinators will screen for potential participants from the electronic medical record. Once a potential research candidate is identified, the investigators and/or research coordinators will discuss the research protocol with the provider (doctor, nurse, or house staff) taking care of the SAR/LTC resident and request permission to include him/her in the trial. If the primary provider agrees to include the resident in the trial, then he/she will be invited to participate in the study. Subjects will be approached by phone or in their facility room to find out their interested. If the potential candidate is interested, they will be provided with sufficient information on the practice of glucose monitoring before providing written consent. If the primary team deems the resident is not able to give informed consent then we will approach the legal representative (durable power of attorney for health care, court appointed guardian for health care decisions, spouse, or adult child) by phone. In this case, a verbal consent will be obtained, and a full copy of the consent will be provided by email or regular mail. The process of obtaining informed consent will follow the standard procedures of Emory University. This protocol will be submitted for approval by the Emory IRB.

Participation in this study is voluntary. Participants will receive one hundred dollars (\$100.00) during the LTC stay. Total compensation will be one hundred dollars (\$100).

## 14. Withdrawal of Participants

Participants may withdraw from the study if they decided to. They also will have the right to request that any data was collected to be removed by contacting members of the research team.

## 15. Risks to Participants

### Potential Risk to Human Subjects

**Hypoglycemia.** The risk of hypoglycemia in patients treated with insulin regimens is between 12%–35%. In this study, hypoglycemia is defined as a BG or IG < 70 mg/dL. Clinical significant hypoglycemia is defined as BG or IG < 54 mg/dl. Severe hypoglycemia is defined as BG < 40 mg/dL.

**Use of CGM.** No major risks are expected with the use of the CGM device. Pain and bleeding with insertion is minimal. Skin irritation may occur in those sensitive to adhesives.

### Protection against Risks

We will follow safeguards to minimize the risk to our subjects: a) we will carefully monitor capillary BG at the bedside using a hand-held glucose meter, b) only experienced nurses/or phlebotomist will draw blood samples. To prevent significant clinical events, no patients with history of significant liver, renal impairment or cardiac failure will be recruited in this study.

We expect that approximately 20-30% in insulin and sulfonylurea treated patients will experience one or more episodes of hypoglycemia. To minimize the risk of hypoglycemia, the starting dose will be adjusted following a protocol that has been shown effective on insulin adjustment. To avoid hypoglycemia, the total daily dose of insulin will be decreased by 10% for BG between 70-99 mg/dl and by 20% after each episode of hypoglycemia (BG < 70 mg/dl).

**CGM – alarms and hypoglycemia protocol.** We will use a Dexcom CGM device with a modified transmitter able to store and transmit glucose data to different devices including a notebook/IPAD or computer desk located at the nursing station. The use of hypoglycemia alarm set at 85 mg/dl will alert nursing staff and providers that a patient maybe at risk of hypoglycemia. If this occurs, the nursing staff will meet patient in the room to assess clinical status and signs/symptoms of hypoglycemia and will perform a POC glucose testing to confirm glucose values. In addition, a carbohydrate load of 15 grams will be provided to patients as per hospital protocol to avoid hypoglycemia.

**Hyperglycemia alarm** will be set at 300 mg/dl to alert the nursing staff and providers of the risk of clinically significant hyperglycemic complication. If this occurs, the nursing staff will meet patient in the room to assess clinical status and will perform a POC glucose testing to confirm glucose values. If BG > 300 mg/dl, nursing staff will communicate this high glucose value to the primary care team. The primary care team will review patient record and insulin administration prior to determining need for additional corrective rapid-acting insulin. If patient has received corrective insulin within the past 2 hours, additional correction will not be given, and the blood

sugar will be re-checked in 1 hour. If the glucose value continues to rise with a rise indicated by CGM trend arrow, then additional corrective insulin will be given at that time.

Hypoglycemia management: If the patient is awake, 25 ml (1/2 amp) will be given IV or oral juice/snack (crackers) as per protocol. If the patient is not awake: 50ml (1 amp) will be given STAT. Blood glucose levels will be repeated in 15 minutes and dextrose administration will be repeated as needed for values < 70 mg/dl.

Insertion of the CGM sensor will be performed per manufacturer instructions, and following an aseptic technique. After insertion of the sensors, providers will ensure proper hemostasis is achieved. Sensors will be removed if prolonged bleeding or severe pain occurs.

## **16. Potential Benefits to Participants**

Subject participating in the standard group will not receive any direct benefits during the LTC stay, since treatment decision will be made based on POC BG (standard of care). Patients in the intervention group of CGM-GTS will also have a POC in the morning, but will benefit of 24/7 glucose monitoring to assess glycemic control. In addition, CGM with alarm may reduce the risk of hypoglycemia.

## **17. Compensation to Participants**

Participants will receive one hundred dollars (\$100.00) during the LTC stay. Total compensation will be one hundred dollars (\$100). Compensation will be provided via ClinCard.

## **18. Data Management and Confidentiality**

In order to assure each subject's confidentiality, data collected under this protocol will be coded and stored in a secure locked file cabinet with access limited to those directly related to the conduct of this study. Electronic versions of these data will be stored on a limited access, password protected, secure server with coded patient identifiers. Study participants will be assigned a code number that will be linked to their name. Only study personal will have access to the linked name-code key.

### Confidentiality

All data and records generated during this study will be kept confidential in accordance with Institutional policies and HIPAA on subject privacy. The Principal investigator and other study personnel will not use data or PHI for any purpose other than conduction of the study. All PHI used will be de-identified and coded by the Principal investigator or designee. The code will be kept in a password protected computer file. PHI will be disclosed when required for audit by regulatory agency.

Information from medical records and from the procedures, interviews and tests that are part of this research will be collected. The personal information will be kept private and confidential. Absolute confidentiality cannot be guaranteed. Personal information may be disclosed if required by law. The results of this study may be shown at meetings or published in journals to inform

other doctors and health professionals. Subject identity will be kept private in any publication or presentation about the study. People and organizations that may inspect and/or copy research records to assure the quality of the data and to analyze the data include:

- Medical staff who are directly or indirectly involved in patients' care related to this research;
- People who oversee or evaluate research and care activities at Emory University
- People from agencies and organizations that perform independent accreditation and oversight of research;
  - Emory offices that are part of the Human Research Participant Protection Program and those that are involved in study administration and billing. These include the Emory IRB, the Emory Research and Healthcare Compliance Offices, and the Emory Office for Clinical Research
  - Government agencies that regulate the research
  - Public health agencies
  - Research monitors and reviewer
  - Accreditation agencies

Data management and statistical analysis:

The present aims of this RCT is to investigate whether the Dexcom G6 CGM with Glucose Telemetry System (CGM-GTS) with hypoglycemia alarm may reduce the risk of hypoglycemia < 70 mg/dl (safety outcome) and improve glycemic control as measured by the percent of time in range (TIR) 70-180 mg/dl (efficacy end-point) in patients with T2D in subacute and long-term skilled nursing care facilities. Patients in the standard of care group will wear a blinded CGM and receive POC testing before meals and bedtime, with providers adjusting oral agents or insulin dose based on POC results. Patients in the intervention CGM group will have a single daily fasting POC testing and will wear a real-time Dexcom G6 with GTS, and providers will adjust oral or insulin therapy based on CGM-GTS profile information. [name], PhD at the School of Public Health at Emory University will conduct statistical analyses.

For the safety endpoint, we will first compare the proportions of patients who have at least one episode of hypoglycemia by POC and by CGM. We will first perform nonparametric comparisons of the rate of hypoglycemia based on a two-sided Chi-square test (or Fisher's exact test in the presence of low incidence rates), followed by the Cochran-Mantel-Haenszel test, which adjusts for the potential center effect. Then we will perform univariate Poisson regression (or Negative Binomial regression) to assess whether there is any difference in the number of clinically significant hypoglycemia events between the two treatment groups. We will further conduct multivariate Logistic regression, Poisson regression (or Negative Binomial regression) to estimate the difference in the rate and frequency of hypoglycemia while adjusting for potential confounders. A glucose value < 70 mg/dl is considered as hypoglycemia requiring a nurse-driven response; thus, a BG <70 mg/dl will be used for sample size calculation. Data from Singh et al a reduction of hypoglycemia was reported comparing the CGM/GTS system than POC (Singh et al 2020) per patient (0.67 episodes per patient, 95% CI 0.34-1.30

versus 1.69 episodes per patient, 95% CI 1.11-2.58,  $p= 0.024$ ) . Based on the results of the recent glargine U100 vs U300 study using CGM monitoring in the hospital, 56% had CGM BG readings <70 mg/dl (vs 14% with POC testing-standard of care), it is reasonable to assume 60% of resident on LTC facilities will experience one or more BG < 70 mg/dl by CGM. If we assume that 35% in the standard of care group will have at least one BG <70 mg/dl (based on linagliptin LTC study) , using one-sided, two-sample t-tests, we require we will need 70 patients per group to achieve 80% power.

Hypoglycemia incidence, Rate in the CGM intervention group	30%	35%	40%	45%	50%
Estimated sample size (N/group) for 80% power	49	70	107	186	407

For the efficacy endpoint, we will compare mean daily glucose levels measured by CGM or POC, and percent TIR measured by CGM between treatment groups by nonparametric Wilcoxon-tests or two-sample t-tests, and by multivariate linear regression, which adjusts for other potential confounders such as age, gender, BMI, center, and admission HbA1c. A logarithm transformation may be employed to make the data better conform to the normality assumption. When conducting multivariate regression analyses, we will apply standard variable selection and model checking procedures to decide the final model. Stepwise, backward, or forward model selection strategy will be adopted to determine the variables to be included in the final model. Standard diagnostic and model checking procedures, such as deviance residual plot and Hosmer- Lemeshow test, will be applied to examine the fit of the developed models. To show non-inferiority between POC and CGM in terms of glycemic control, we set the equivalence margin of 18 mg/dl (1 mosm/l), from a view that a difference <18 mg/dl is usually not considered as clinically significant . Based on the results from our recent CGM trials , it is reasonable to assume the standard deviation of mean daily BG is bounded above by 45 mg/dl. Assuming the true BG difference between the treatment groups is zero, and using one-sided, two-sample t-tests, we require 70 subjects for each treatment group to achieve 80% power.

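### No primary glucose source is named for the hypoglycaemia and mean-glucose comparisons, and POC testing differs by arm, so a between-arm POC result is biased in a direction that cannot be known in advance

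*Combined protocol and SAP*

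**What the plan says.** The source of the glucose values is left open in four places.

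- Section 4 (Study Endpoints) lists hypoglycaemia below 70 and below 54 mg/dl as the safety outcome and names no measurement source.
- Section 15 (Risks to Participants) defines hypoglycaemia as a blood or an interstitial value below 70 mg/dl, with no order of precedence.
- Section 18 (Data management and statistical analysis) says of the safety endpoint: "we will first compare the proportions of patients who have at least one episode of hypoglycemia by POC and by CGM".
- The same section says of glycaemic control "we will compare mean daily glucose levels measured by CGM or POC", and then "To show non-inferiority between POC and CGM in terms of glycemic control, we set the equivalence margin of 18 mg/dl". It does not say which source the non-inferiority test uses.

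Time in range is different: Section 18 ties it to CGM.

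The POC schedule is set by arm. For control: "Patients in the standard of care group will wear a blinded CGM and receive POC testing before meals and bedtime", and "For control group (blinded CGM) CGM alarms are turned off". For the intervention: "Patients in the intervention CGM group will have a single daily fasting POC testing". CGM-GTS residents also have alarm-triggered tests. After the 300 mg/dl alarm, Section 6 says: "If this occurs, the nursing staff will assess clinical status and perform a POC glucose testing to confirm glucose values", and Section 15 (Protection against Risks) agrees. For the 85 mg/dl alarm, Section 15 calls for a confirmatory POC test as well as carbohydrate. Section 6 says only: "Nursing staff will be instructed to provide 15 grams of carbohydrates in response to a hypoglycemia alarm".

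**The concern.** A resident counts as hypoglycaemic by POC only if someone tests while glucose is low. Here the number, timing and reason for testing all differ by arm. Fewer scheduled tests lower the CGM-GTS POC rate. Tests prompted by a low alarm raise it. For a POC mean, a fasting-only schedule samples a different part of the day from four routine tests, and tests triggered at 85 and 300 mg/dl pull the mean in opposite directions. The plan does not limit POC data to times the arms share or allow for the number of tests.

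The choice of source is not minor. The hospital study cited in Section 18 found 56% of patients below 70 mg/dl by CGM against 14% by POC. If the two sources disagree on the primary safety outcome, the plan does not say which result counts, and the choice could be made after both have been seen.

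**Working it through.** **The plan's own figure.** Section 18 plans on 60% against 35% and 70 per group. The continuity-corrected two-proportion formula, two-sided 5%, 80% power, reproduces this:

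- Uncorrected n = [1.96·√(2·0.475·0.525) + 0.842·√(0.60·0.40 + 0.35·0.65)]² / 0.25² = 61.4, so 62.
- Corrected n = (61.4/4)·[1 + √(1 + 4/(61.4·0.25))]² = 69.2, so 70.

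The one-sided test named in the text does not give 70 (49 without the correction, 56 with it); that is a separate matter. What matters here is the source of the two rates. The 60% is stated as a CGM rate. The 35% is referred to the linagliptin long-term care study, which Section 3 describes as measuring glucose before meals. The text gives the 35% to standard of care, while the table beside it lists 35% as a CGM intervention rate. The sample-size paragraph therefore does not settle the source.

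**Hypothetical illustration of the POC comparison.** Assumptions:

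- True glycaemia is identical in the two arms.
- The control POC rate is 35%, used here as an assumed value.
- 60% of residents are low by sensor (Section 18).
- Scheduled tests are independent with equal risk: four a day in control (three meals and bedtime), one in CGM-GTS.
- There are 50 per arm (total of 100 in Section 12; 1:1 is assumed).
- The test is an uncorrected chi-square at two-sided 5% (the level is assumed), by exact binomial enumeration.

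Step 1, scheduled tests only. The CGM-GTS POC rate is q₀ = 1 − (1 − 0.35)^(1/4) = 10.2%.

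Step 2, add alarm tests. Let c be the share of the remaining sensor-low residents whom an alarm-triggered POC test records below 70 mg/dl. Then q = q₀ + (0.60 − q₀)·c.

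Step 3, chance of p < 0.05 with no true difference:

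| c | CGM-GTS POC rate | 50 per arm | 70 per arm | Direction |
|---|---|---|---|---|
| 0 | 10.2% | 87% | 95% | favours CGM-GTS |
| 0.25 | 22.7% | 28% | 37% | favours CGM-GTS |
| 0.50 | 35.1% | 5% | 5% | none |
| 0.75 | 47.6% | 26% | 32% | against CGM-GTS |
| 1 | 60.0% | 73% | 85% | against CGM-GTS |

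Step 4, the point of no bias: c = (0.35 − 0.102)/(0.60 − 0.102) = 0.50.

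**Sensitivity.** With strong clustering of lows within residents (gamma frailty, variance 4), q₀ is 17.4%, the 87% falls to 52% and the sign still reverses as c rises. With a 14% control POC rate, q₀ is 3.7%, rejection runs from 45% in favour to over 99% against, and the point of no bias is c = 0.18. That case pairs a hospital POC rate with a long-term care planning rate and is only a bound.

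**The shared fasting test as a check.** Apply the plan's relative reduction (35/60) to the fasting rates above. 10.2% against 6.0% has about 11% power at 50 per arm; 3.7% against 2.2% has about 4%. The fasting comparison is too weak to be a formal test.

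**The case against.** The plan leans towards CGM. The 60% rate is a CGM rate, time in range is measured by CGM, the SD for the non-inferiority test is drawn from the team's CGM trials, control wears a blinded sensor, and Section 3 says blinded CGM in the earlier telemetry trial served only to collect glucose metrics. A CGM comparison is already planned. These points are fair and make the correction short, but none of them designates a source.

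The phrase naming POC and CGM in the safety analysis could also be a pair of arm labels, because the non-inferiority sentence uses the two terms that way. On that reading no separate POC test is specified, but the source of the hypoglycaemia values is then still unstated, and the blood-or-interstitial definition and the mean-glucose sentence remain open.

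The high-capture rows deserve caution. The 60% is sensor-detected, not proven true hypoglycaemia. The alarm is set at 85 mg/dl and carbohydrate is given, so many confirmatory tests may read above 70. Full capture is an extreme.

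A reader might infer that the POC comparison flatters CGM-GTS because that arm has fewer scheduled tests. The documents do not support a direction: alarm-triggered tests act the other way and their frequency is not given. Nor can a size be put on bias in a POC mean, since the documents give no offset between fasting and all-day values.

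**Conclusion.** The concern holds as an undesignated source combined with POC ascertainment that differs by arm. A between-arm POC comparison run as written reflects testing as well as treatment, in an unknown direction. Under the stated assumptions the false-difference rate at 50 per arm runs from about 87% favouring CGM-GTS, through 5% at about half capture, to about 73% against it at the extreme. These figures show that the sign can change; they are not forecasts.

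A reader might go further and conclude that the trial has no sound primary comparison. That does not follow. The CGM hypoglycaemia comparison and time in range do not depend on the POC schedule; what is missing is the statement that CGM decides. The mean-glucose part carries less weight, because mean daily glucose is in neither endpoint list in Section 4 and appears only in the analysis text. This should be fixed before any comparative result is seen.

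**What to change.** - In Section 4 and in the safety paragraph of Section 18, name CGM (blinded in control, real-time in CGM-GTS) as the source in both arms for the primary hypoglycaemia comparison.
- In the efficacy paragraph of Section 18, name CGM for mean daily glucose and for the 18 mg/dl non-inferiority test.
- Report all POC results by arm descriptively, including the scheduled fasting test that both arms share as a low-power check. Give the number of POC tests and the sensor wear by arm.
- Reconcile the low-alarm response in Section 6 with that in Section 15, since they differ on whether a POC test is done.

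The cost is wording; no device, visit or participant is added. The between-arm POC p-value is lost. The primary result then rests on sensor accuracy (overall MARD about 12.7% for the G6 in the hospital data in Section 3) and on wear. In CGM-GTS the same sensor triggers the alarm and scores the outcome, so a low that it misses is neither acted on nor counted. The fasting POC summary offers some outside view of this, at one time of day only.
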